7.3 Liver safety monitoring

To ensure patient safety and enhance reliability in determining the hepatotoxic potential of an investigational drug, a standardized process for identification, monitoring and evaluation of liver events has to be followed.

The following two categories of abnormalities / adverse events have to be considered during the course of the study (irrespective of whether classified/reported as (S)AE):

- Liver laboratory triggers, which will require repeated assessments of the abnormal laboratory parameter
- Liver events, which are considered as medically significant events, i.e., SAEs and which consist of marked elevations of LFTs and / or pre-specified adverse events. These events will require close observation, follow-up monitoring and completion of the standard base liver CRF pages.

Any liver event which meets the criteria for a “**medically significant**” event should follow the **standard procedures for SAE reporting** as described in [Section 7.2](#).

Please refer to [Table 14-1](#) in [Appendix 2](#) for complete definitions of liver laboratory triggers and liver events.

Every liver laboratory trigger or liver event as defined in [Table 14-1](#) of [Appendix 2](#) should be followed up by the investigator or a designated medically qualified person at the trial site as summarized below. Detailed information is outlined in [Table 14-2](#) in [Appendix 2](#).

For the liver laboratory trigger:

- Repeating the LFT within 24 hours to confirm elevation.

These LFT repeats can be performed at a local laboratory to monitor the safety of the subject. If a liver event is subsequently reported, any local LFTs previously conducted that are associated with this event should be reported on the liver CRF pages.

Repeat laboratory tests must be entered on the appropriate unscheduled local laboratory CRF page.

- If the elevation is confirmed, close observation of the patient will be initiated, including consideration of treatment discontinuation if deemed appropriate.

For the liver events:

- Repeating the LFT to confirm elevation as appropriate
- Discontinuation of the investigational drug if appropriate
- Hospitalization of the patient if appropriate
- A causality assessment of the liver event via exclusion of alternative causes (e.g., disease, co-medications)
- An investigation of the liver event which needs to be followed until resolution.

These investigations can include serology tests, imaging and pathology assessments, hepatologist’s consultancy, based on investigator’s discretion. All follow-up information, and the procedures performed must be recorded on appropriate CRF pages, including the liver event overview CRF pages.

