Based on the pre-specified criteria (Table 3-1) and the review of the liver safety data by a safety review committee, the recruitment in Cohort 5 may be stopped and a lower dose of KAE609 i.e. 110 mg may be selected for Cohort 6.

The study could be stopped after Cohort 5 if there is no added advantage for dosing the patients with 225 mg single dose from the perspective of future clinical development of KAE609 and its subsequent use in clinical practice.

Figure 3-1 Study KAE609A2202 diagram

Given the expected sub-therapeutic efficacy of the doses of KAE609 in the first 2 cohorts, a smaller number (N=10) of patients will be included (10 mg Single Dose (SD), 25 mg SD and 10 mg 3 Days) to detect potential LFT increases. In the subsequent cohorts a higher number (N=20) of patients will be included. All patients will be followed up for 4 weeks with close monitoring in an inpatient setting for at least the first 3 days (Study Day 4) for efficacy and safety followed by outpatient monitoring up to Study Day 29.

Patients will remain in the hospital under close supervision until they are discharged by the investigator or designee on Study Day 4. To be discharged, patients should present 2 consecutive study assessments with negative blood smear for *P. falciparum* parasites and clearance of fever. At the discretion of the investigator, patients may remain in hospital for additional days if needed.

Coartem® (Artemether-Lumefantrine) will be used as rescue medication in KAE609 patients meeting the treatment failure criteria (see Section 5.5.6). Any patient on KAE609 who does not need rescue medication up to Study Day 28 will be given Coartem at the end of the study (Study Day 29) and will be followed as per standard medical care.

Visits to assess safety and efficacy will be scheduled during the follow-up period as described in the assessment schedule table (Table 6-1). If malaria symptoms re-emerge outside the scheduled study visits, patients will be instructed to contact the investigator as soon as possible. For severe malaria, rescue medication according to local guidance will be used.

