$> 8 \times \text{ULN}$	
 • Discontinue the study treatment immediately • Repeat LFTs within 24h • Hospitalize if clinically appropriate • Establish causality • Complete liver CRF • Report to Novartis as an SAE 	ALT, AST, TBL, Alb, PT/INR, ALP and GGT until resolution ^c (frequency twice a week until resolution, stabilize or return to within baseline values)
$> 3 \times \text{ULN}$ and $\text{INR} > 1.5$	
 • Discontinue the study treatment immediately • Repeat LFTs within 24h • Hospitalize, if clinically appropriate • Establish causality • Complete liver CRF • Report to Novartis as an SAE 	ALT, AST, TBL, Alb, PT/INR, ALP and GGT until resolution ^c (frequency twice a week until resolution, stabilize or return to within baseline values)

Criteria	Actions required	Follow-up monitoring
> 5 to ≤ 8 × ULN	
 Repeat LFT within 24 hours If elevation persists, continue follow-up monitoring If elevation persists for more than 2 weeks, discontinue the study drug Establish causality Complete liver CRF Report to Novartis as an SAE 	ALT, AST, TBL, Alb, PT/INR, ALP and GGT until resolution ^c (frequency twice a week until resolution, stabilize or return to within baseline values)
> 3 × ULN accompanied by symptoms ^b	
 Discontinue the study treatment immediately Repeat LFT within 24 hours Hospitalize if clinically appropriate Establish causality Complete liver CRF Report to Novartis as an SAE 	ALT, AST, TBL, Alb, PT/INR, ALP and GGT until resolution ^c (frequency twice a week until resolution, stabilize or return to within baseline values)
> 3 to ≤ 5 × ULN (patient is asymptomatic)	
 Repeat LFT within 48 hours If elevation is confirmed, initiate close observation of the patient 	Investigator discretion Monitor LFT within 1 to 4 weeks
ALP (isolated)		
> 2 × ULN (in the absence of known bone pathology)	
 Repeat LFT within 24 hours If elevation persists, establish causality Complete liver CRF Report to Novartis as an SAE 	Investigator discretion Monitor LFT within 1 to 4 weeks or at next visit
TBL (isolated)		

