> 2 × ULN (in the absence of known Gilbert syndrome)	
 Repeat LFT within 24 hours If elevation persists, discontinue the study drug immediately Hospitalize if clinically appropriate Establish causality Complete liver CRF Report to Novartis as an SAE 	ALT, AST, TBL, Alb, PT/INR, ALP and GGT until resolution ^c (frequency twice a week until resolution, stabilize or return to within baseline values) Test for hemolysis (e.g., reticulocytes, haptoglobin, unconjugated [indirect] bilirubin)
> 1.5 to ≤ 2 × ULN (patient is asymptomatic)	
 Repeat LFT within the next week If elevation is confirmed, initiate close observation of the patient 	Investigator discretion Monitor LFT within 1 to 4 weeks or at next visit
Preferred terms		
Jaundice	
 Discontinue the study treatment immediately Hospitalize the patient Establish causality Complete liver CRF Report to Novartis as an SAE 	ALT, AST, TBL, Alb, PT/INR, ALP and GGT until resolution ^c (frequency twice a week until resolution, stabilize or return to within baseline values)
Any AE potentially indicative of a liver toxicity* - severe events only SMQ AE	
 Consider study treatment discontinuation Hospitalization if clinically appropriate Establish causality Complete liver CRF Report to Novartis as an SAE 	Investigator discretion

Criteria	Actions required	Follow-up monitoring

*These events cover the following: hepatic failure, fibrosis and cirrhosis, and other liver damage-related conditions; the non-infectious hepatitis; the benign, malignant and unspecified liver neoplasms
 
^aElevated ALT/AST > 3 × ULN and TBL > 2 × ULN but without notable increase in ALP to > 2 × ULN
 
^b(General) malaise, fatigue, abdominal pain, nausea, or vomiting, or rash with eosinophilia
 
^cResolution is defined as an outcome of one of the following: (1) return to baseline values, (2) stable values at three subsequent monitoring visits at least 2 weeks apart, (3) remain at elevated level after a maximum of 6 months, (4) liver transplantation, and (5) death.
 
Alb: albumin; PT: prothrombin time.
		

15 Appendix 3: Specific Renal Alert Criteria and Actions

Table 15-1 Specific Renal Alert Criteria and Actions

Serum Event	
Serum creatinine increase 25 – 49% compared to baseline	Confirm 25% increase after 24-48h Follow up within 2-5 days

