**Table 5-5 Analysis visit windows based on study days alone**

Analysis Visit	Target Day	Analysis window for assessment group		
		Vital signs/ Chemistry/ Hematology	Urinalysis	Pregnancy
Baseline	1	Up to Day 1	Up to Day 1	up to day 1
Day 2	2	Day 2	Day 2-3	NA
Day 3	3	Day 3	NA	NA
Day 4	4	Day 4	NA	NA
Day 5	5	Day 5 - 6	Days 4-13	NA
Day 8	8	Day 7 – 9	NA	NA
Day 11	11	Day 10 – 13	NA	NA
Day 15	15	Day 14 – 16	Day 14 – 16	NA
Day 22	22	Day 17 – 25	NA	NA
Day 29/End of study	29	Day 26 and above	Day 17 and above	Day 2 and above

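### The protocol gives two repeat deadlines for the same liver laboratory triggers, and two bilirubin thresholds for SAE reporting, without saying which prevails

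*Protocol*

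**What the plan says.** **Repeat testing.** Section 7.3 of the protocol sends the reader to Table 14-1 "for complete definitions of liver laboratory triggers and liver events". That table has two laboratory triggers: ALT or AST above 3 and up to 5 x ULN, and total bilirubin (TBL) above 1.5 and up to 2 x ULN. For any such trigger Section 7.3 prescribes "Repeating the LFT within 24 hours to confirm elevation". It presents its follow-up steps "as summarized below. Detailed information is outlined in" Table 14-2. For asymptomatic patients in the same two bands, Table 14-2 says "Repeat LFT within 48 hours" (ALT/AST) and "Repeat LFT within the next week" (TBL).

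**Bilirubin as an SAE.** Appendix 1 lists hepatic findings that go to the sponsor as SAEs within 24 hours, among them TBL above twice the baseline value. Table 14-1 gives an otherwise matching list of liver events to be reported as SAEs, but its bilirubin line is TBL above twice ULN, with known Gilbert syndrome excepted; Table 14-2 repeats that threshold. Sections 6.5.4 and 7.1 point sites to Appendix 1, and Section 7.3 points them to Table 14-1.

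**The concern.** A summary may leave out detail, but it should not state a different deadline from the table it summarises. A site that follows Table 14-2 to the letter can breach Section 7.3.

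The two SAE lists match line by line except for bilirubin, which looks more like a drafting slip than two intended rules. A site that works from one list will miss cases that the other captures.

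Hepatic safety is the primary objective, and Section 7.3 sets out to standardise liver follow-up. Two things are at stake: how soon an outpatient bilirubin rise is confirmed, and whether the bilirubin SAE count depends on which page a site used. SAEs are a listed output for the safety review committee (SAP Table 2-6).

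**Working it through.** The plan states no figure to reproduce here. The check compares the texts and adds simple arithmetic.

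**1. Repeat timing**

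Inputs: deadlines of 24 hours (Section 7.3), 48 hours and one week (Table 14-2). Target days come from SAP Table 5-5, in the column headed "Vital signs/ Chemistry/ Hematology": 2, 3, 4, 5, 8, 11, 15, 22 and 29. The assessment grid (protocol Table 6-1) is not in the text available for this review, so I assume that chemistry is drawn on each of these days.

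Gaps between successive days: 1, 1, 1, 3, 3, 4, 7, 7. For triggers first seen on Days 2 to 4 the next sample is a day away, and the deadlines barely differ. From Day 5 onwards:

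| Trigger first seen | Next scheduled sample | ALT/AST: scheduled sample within 48 h? | TBL: scheduled sample within a week? | Possible extra TBL delay (gap − 1 day) |
|---|---|---|---|---|
| Day 5 | 3 days | no | yes | 2 days |
| Day 8 | 3 days | no | yes | 2 days |
| Day 11 | 4 days | no | yes | 3 days |
| Day 15 | 7 days | no | yes | 6 days |
| Day 22 | 7 days | no | yes | 6 days |

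For ALT/AST, both deadlines need an unscheduled sample on all five days, at 24 or 48 hours. For TBL, Section 7.3 needs an unscheduled sample each time and Table 14-2 needs none. No scheduled visit follows Day 29.

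After a minimum inpatient stay to Day 4, patients are "followed by outpatient monitoring up to Study Day 29". Days 5, 8 and 11 lie within the 14 days in which Section 3.1 expects liver tests to peak.

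**2. Bilirubin SAE threshold**

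Let b be baseline TBL in multiples of ULN. The Appendix 1 threshold is 2b; the Table 14-1 threshold is fixed at 2. Exclusion criterion 6 (Section 4.2) allows b up to 2 when AST and ALT are not above ULN. The values of b are illustrative, because the documents give no baseline bilirubin distribution.

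| b | Appendix 1 threshold (2b) | Range where the lists disagree (x ULN) |
|---|---|---|
| 0.5 | 1.0 | above 1.0 to 2.0: Appendix 1 only |
| 0.75 | 1.5 | above 1.5 to 2.0: Appendix 1 only (the whole trigger band) |
| 0.9 | 1.8 | above 1.8 to 2.0: Appendix 1 only |
| 1.0 | 2.0 | none, Gilbert syndrome aside |
| 1.5 | 3.0 | above 2.0 to 3.0: Table 14-1 only |
| 2.0 | 4.0 | above 2.0 to 4.0: Table 14-1 only |

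Below b = 0.5, the Appendix 1 threshold lies inside the normal range.

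Appendix 1 speaks of adverse events. Under Section 7.1 a laboratory value is one only if it produces signs or symptoms, is clinically significant or needs therapy. Take an asymptomatic rise from 0.7 to 1.8 x ULN that the investigator judges clinically significant: 1.8 / 0.7 = 2.57 times baseline. Appendix 1 makes it an SAE; Table 14-2 makes it a trigger to be repeated within a week. In the other direction, a rise from 1.5 to 2.5 x ULN is an SAE under Table 14-1 (known Gilbert syndrome aside) but does not reach the Appendix 1 bilirubin line (3.0 x ULN).

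**The case against.** The strongest reply is that the rules can be followed together. A repeat within 24 hours also meets the 48-hour and one-week limits, and a site applying both SAE lists reports on either threshold. Section 7.3 also describes Table 14-2 as the detail, which suggests that the table governs. The longer intervals cover asymptomatic patients only: ALT/AST above 3 x ULN with symptoms already requires a 24-hour repeat and an SAE report.

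Little also hangs on the timing. KAE609 is given for at most three days and the last Coartem dose is at 60 hours, so a later repeat cannot change study dosing. The escalation criteria use the maximum post-baseline ALT/AST, not a confirmed repeat. The committee also sees liver enzyme abnormalities and eDISH plots, which use peak bilirubin, so a rise can reach it without an SAE report. Finally, whether a laboratory value becomes an SAE involves medical judgment under any threshold.

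All of this stands and limits the consequence. It does not settle which rule applies. Calling one text the detail does not cancel a different explicit deadline in the other, and the inclusive reading of the SAE lists protects only sites that consult both.

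**Conclusion.** The concern holds. Both conflicts are in the current protocol text, and neither is resolved elsewhere in the documents. The consequence is confined to repeat timing, mainly in outpatients, and to the bilirubin SAE count. TBL confirmation can come 2 to 6 days later under one rule than under the other. The SAE lists disagree in opposite directions below and above a baseline of 1 x ULN.

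The primary endpoint, the ALT/AST escalation criteria and the TBL counts in SAP Table 2-2 do not change. The timing figures assume that chemistry is drawn on every target day in SAP Table 5-5. The number of patients affected cannot be calculated, because the documents give no frequency for such rises.

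**What to change.** 1. **One interval per trigger.** Either change the two Table 14-2 rows to 24 hours, or remove the interval from Section 7.3 and refer to Table 14-2. The first costs about one unscheduled outpatient sample per TBL trigger first seen on Day 5, 8, 11, 15 or 22. The second adds no samples.

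2. **One bilirubin SAE criterion in both appendices.** My preference is: *TBL above 2 x ULN unless Gilbert syndrome is known, or TBL above 2 x baseline and above ULN*. This closes the gap in both directions and leaves out doublings within the normal range. It would add some reports at sites now using Table 14-1 alone; the number cannot be estimated from the documents. The alternative is the 2 x ULN rule with the Gilbert exception in both places. That matches Table 14-1 and the cut-off in SAP Table 2-2, but gives up the only baseline-relative bilirubin rule.

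3. **If data collection is complete** (the SAP history records an update after database lock), no new analysis is needed. Read the bilirubin SAE count beside the count of TBL above 2 x ULN already planned in SAP Table 2-2.

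Items 1 and 2 need a protocol wording change and a notice to sites.

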7.4 Renal safety monitoring

The following two categories of abnormal renal laboratory values have to be considered during the course of the study:

- Serum event:
 - confirmed (after ≥ 24 h) increase in serum creatinine of $\geq 25\%$ compared to baseline during normal hydration status
- Urine event
 - new onset ($\geq 1+$) proteinuria; confirmed by doubling in the urinary albumin-creatinine ratio (ACR) or urinary protein-creatinine ratio (PCR) (if applicable)
 - new onset ($\geq 1+$), hematuria or glycosuria

Every renal laboratory trigger or renal event as defined in [Table 15-1](#) in [Appendix 3](#) should be followed up by the investigator or designated personnel at the trial site as summarized in [Appendix 3](#).

7.5 Reporting of study treatment errors including misuse/abuse

Medication errors are unintentional errors in the prescribing, dispensing, administration or monitoring of a medicine while under the control of a healthcare professional, patient or consumer (European Medicines Agency (EMA) definition).

Misuse refers to situations where the medicinal product is intentionally and inappropriately used not in accordance with the protocol.

Abuse corresponds to the persistent or sporadic, intentional excessive use of a medicinal product, which is accompanied by harmful physical or psychological effects.

Study treatment errors and uses outside of what is foreseen in the protocol will be collected in the DAR eCRF irrespective of whether or not associated with an AE/SAE and reported to Safety only if associated with an SAE. Misuse or abuse will be collected and reported in the safety database irrespective of it being associated with an AE/SAE.

Table 7-1 Guidance for capturing the study treatment errors including misuse/abuse

Treatment error type	Document in Dose Administration Record (DAR) eCRF (Yes/No)	Document in AE eCRF	Complete SAE form
Unintentional study treatment error	Yes	Only if associated with an AE	Only if associated with an SAE
Misuse/Abuse	Yes	Yes	Yes, even if not associated with a SAE

7.6 Pregnancy reporting

To ensure patient safety, each pregnancy occurring after signing the informed consent must be reported to Novartis within 24 hours of learning of its occurrence. The pregnancy should be followed up to determine outcome, including spontaneous or voluntary termination, details of

the birth, and the presence or absence of any birth defects, congenital abnormalities, or maternal and/or newborn complications.

Pregnancy must be recorded on the Pharmacovigilance Pregnancy Form and reported by the investigator to the local/regional Novartis CMO & PS Department. Pregnancy follow-up should be recorded on the same form and should include an assessment of the possible relationship to the study treatment.

Any SAE experienced during the pregnancy and unrelated to the pregnancy must be reported on an eSAE form/paper SAE form (as applicable).

Pregnancy outcomes should be collected for the female partners of any males who took study treatment in this study. Consent to report information regarding these pregnancy outcomes should be obtained from the female partner.

8 Data review and database management

8.1 Site monitoring

Before study initiation, at a site initiation visit or at an investigator's meeting, a Novartis representative will review the protocol and eCRFs with the investigators and their staff. During the study, the field monitor will visit the site regularly to check the completeness of patient records, the accuracy of entries on the eCRFs, the adherence to the protocol and to Good Clinical Practice (GCP), the progress of enrollment, and to ensure that study drugs are being stored, dispensed, and accounted for according to specifications. Key study personnel must be available to assist the field monitor during these visits. Continuous remote monitoring of each site's data may be performed by a centralized Novartis CRA organization. Additionally, a central analytics organization may analyze data & identify risks & trends for site operational parameters, and provide reports to Novartis Clinical Teams to assist with trial oversight.

The investigator must maintain source documents (archival and storage) for each patient in the study, consisting of case and visit notes (hospital or clinic medical records) containing demographic and medical information, laboratory data, ECGs, and the results of any other tests or assessments as per ICH-GCP standards. All information on eCRFs must be traceable to these source documents in the patient's file. The investigator must also keep the original informed consent form signed by the patient (a signed copy is given to the patient).

The investigator must give the monitor access to all relevant source documents to confirm their consistency with the eCRF entries. Novartis monitoring standards require full verification for the presence of informed consent, adherence to the inclusion/exclusion criteria, documentation of SAEs, and the recording of data that will be used for all primary and safety variables. Additional checks of the consistency of the source data with the eCRFs are performed according to the study-specific monitoring plan. No information in source documents about the identity of the patients/subjects will be disclosed.

8.2 Data collection

Designated investigator staff will enter the data required by the protocol into the eCRFs using fully validated software that conforms to 21 US Code of Federal Regulations (CFR) Part 11 requirements and into the OC/RDC. Designated investigator site staff will not be given access to the system until they have been trained. Automatic validation programs check for data discrepancies during and after data entry and, by generating appropriate error messages, allow the data to be confirmed or corrected online by the designated investigator site staff. The Investigator must certify that the data entered into the eCRFs are complete and accurate. After database lock, the investigator will receive a CD-ROM or paper copies of the patient data for archiving at the investigational site.

All data captured for this study will have an external originating source (either written or electronic), the eCRF is not considered as source.

